### **8.2.3.1.3. Analysis of deaths**

There are the following 2 definitions for deaths, and the analysis will be performed for each of them. As the primary evaluation, deaths (overall observation period) will be used.

- Deaths (overall observation period): Deaths (overall observation period) are patients who die from the date of the initiation of treatment to the date of the completion or discontinuation of follow-up.

- Deaths (treatment period): Deaths (treatment period) are patients in whom deaths developed from the date of the initiation of treatment to the date of the completion of treatment.

Other definitions used in the comparison of deaths are shown in [Table 7](#).

**Table 7. Definitions in the Comparison of Deaths**

Term	Definition
Survivors	Patients who do not correspond to the each definition of deaths
Time to death (overall observation period)	Date of the death - date of the initiation of treatment + 1
Censoring period for survivors (overall observation period)	Xeljanz group: Date of completion or discontinuation of follow-up - date of the initiation of treatment + 1
Time to death (treatment period)	Xeljanz group: Date of the death - date of the initiation of treatment + 1
Censoring period for survivors (treatment period)	Date of the completion of treatment - date of the initiation of treatment + 1

• **Mortality rate**

The number of patients with deaths in each group, incidence, and the 95% confidence interval will be calculated in accordance with [Section 8.1.5](#).

In addition, the incidence ratio and the 95% confidence interval and the difference in incidence rate and the 95% confidence interval will be calculated.

- **Incidence proportion of deaths**

The number of patients with deaths in each group, the incidence proportion, and the 95% confidence interval will be calculated in accordance with [Section 8.1.5](#).

In addition, the ratio of incidence proportion and the 95% confidence interval and the difference in incidence proportion and the 95% confidence interval will be calculated.

- **Analysis of time to death**

Time to death in each group will be summarized in accordance with [Section 8.1.4](#). As for the censoring period insurvivors, [Table 7](#) will be followed.

- **SMR**

Using the number of deaths in each group, the SMR and its 95% confidence interval with the Japanese as the reference population are calculated according to Section 8.1.6. The expected number of deaths is calculated using the population and deaths by gender, age and calendar year. If there is no reference population and death in the applicable calendar year, use the reference population and death by gender and age in the latest year.

Similarly, it is calculated for non MTX adherent safety analysis set.

For Japanese data, refer to the general counter of e-Stat official statistics, and calculate the expected number of deaths using the population and the number of deaths in the Vital Statistics Survey.

CC1 [REDACTED]  
[REDACTED]  
C [REDACTED]  
C [REDACTED]  
I [REDACTED]

CCI [REDACTED]

[REDACTED]

• CCI [REDACTED]

[REDACTED]

CCI [REDACTED].

• CCI [REDACTED]

[REDACTED]

CCI [REDACTED]

CCI [REDACTED]

CCI [REDACTED]

C

C

I

CCI

CCI

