#### [Rationale for sample size]

The incidence of malignant tumor associated with Xeljanz in a domestic long-term administration study (Study No. A3921041) was 1.16 (/100 person-year). The drop-out rate in clinical studies was 31% among subjects who transferred from the domestic Phase II study (Study No. A3921039) to the domestic long-term administration study (Study No. A3921041) (treatment period: approximately 3 years), and 14% among subjects who transferred from another domestic Phase II study (Study No. A3921040) (treatment period: approximately 1.4 years); based on which, the drop-out rate at the completion of 3-year observation in daily medical practice is estimated to be approximately 50%.

If 4000 patients were to be enrolled in the Xeljanz group, the target events should be confirmable in 104 patients based on the incidence of malignant tumor in Japanese subjects, which was 1.16 (/100 person-year).

Next, assuming that 4000 patients would be enrolled in the Xeljanz group and the incidence of malignant tumor in the control group would be equivalent to the Xeljanz group, at least 2000 subjects would need to be enrolled in the control group in order to enable a statistically appropriate inter-group comparison; thus, a sample size of 2000 subjects was selected for control.

Depending on the progress of registration, if the registered number of patients in either group significantly exceeds the above number earlier than the other group, a sample size with 3-year observation period can be changed to the combination of a sample size for whom the degree of statistical accuracy is maintainable if it is compared with 4000

patients in the Xeljanz group and 2000 patients in the control group (see the Appended Table). Also, the registration period for patients in the inter-group comparison needs to be the same.

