### 6.3 Contract and logistics

A contract for this Surveillance must be concluded in writing with the head of each site. Contract templates of surveillance site shall be used if available.

[1] The Medical Representative (hereinafter referred to as "MR") shall provide Xeljanz Proper-use Information to doctors, pharmacists, and other relevant site staff who will handle/use Xeljanz.

[Safety information kit]

Product Summary, Proper Use Guide, explanation of "Precautions" for new pharmaceuticals, literature for use by patients, package inserts, etc.

[2] Sponsor will explain the proper use of Xeljanz to each investigator taking part in this Surveillance; after which, the investigator will sign or name/seal the "Confirmation of Cooperation to Surveillance", and submit it to the MR (this document is also required when the investigator is relocated to another site).

[Confirmation of Cooperation to Surveillance]

- Cooperation to diagnosis and treatment of serious infection, tuberculosis and malignant tumor
- Requirements for sites and doctors
- Other relevant items requiring confirmation
- Signature or name/seal of the investigator taking part in this Surveillance

[3] Upon receiving "Confirmation of Cooperation to Surveillance," a contract for this Surveillance will be concluded between the site and Sponsor.

[4] The sample size ratio between the Xeljanz group and the control group to be specified in the contract will be in principle 2 to 1. However, depending on the conditions at the medical facility, the case ratio may be adjusted between 2:1 and 1:1.

[5] Sponsor, upon confirming the conclusion of contract for this Surveillance, shall set up logistics necessary to deliver Xeljanz to the site.

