### 2.1. Study Design

This survey is a non-interventional study that includes patients who received Xeljanz Tablets (hereinafter referred to as Xeljanz) (Xeljanz group) and patients who started medications for rheumatoid arthritis other than Xeljanz (hereinafter referred to as control drugs) (control group) among patients with uncontrolled rheumatoid arthritis despite the continued use of methotrexate (hereinafter referred to as MTX) at a dose exceeding 8 mg/week for at least 3 months in the cohort.

The control group will include Xeljanz-naive patients, and clinical trial participants are not allowed to be registered in the control group.

<Scheduled number of patients to be investigated>

*Target sample size: Subjects who meet the conditions in “2. Subjects” for each group and the sample size is shown below.*

*1) Xeljanz group: 4000 subjects for safety analysis*

The target sample size is set to be 4000 subjects by adding a certain sample size a) b) exceeding 3000 subjects beginning from the start of registration (3-year observation) to the subsequent number of subjects (6-month observation period). See “6.5 observation period” for more information. However, even if Xeljanz is administered to subjects who do not meet the conditions described in “2. Subjects” for inevitable reason(s), while such subjects will not be included in the above sample size, the request to enroll subjects and complete survey forms will be made for subjects in the Xeljanz group for the sake of all-cases survey.

*2) Control group: A certain sample size a) b) exceeding 2000 subjects for safety analysis*

*[Remarks]*

*a) The sample size in both groups will be set to be the number of subjects for whom the degree of statistical accuracy described in [Rationale for sample size] is maintainable. See the Appendix for more information.*

*b) The registration period until a certain sample size is reached will be the same period for both groups.*

<Rationale for the scheduled number of patients to be investigated>

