#### **4. HYPOTHESES AND DECISION RULES**

Since this survey is not a confirmatory study, statistical tests will be exploratory. Unless otherwise specified, tests will be 2-sided and the significance level will be 5%. A 2-sided confidence interval will be used for interval estimation, and the confidence coefficient will be 95%.

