### 6.3. Covariates

For both the Xeljanz and control groups, candidate covariates related to the development of malignant tumors and serious infections are shown below.

Covariates	Malignant tumor	Serious infection
Sex	○	○
Age	○	○
Weight	○	○
Stage of rheumatoid arthritis	○	○
Class of rheumatoid arthritis	○	○
Duration or disease	○	○
Past history (infection)	×	○
Past history (malignant tumor)	○	×
Past history (lung disorder)	×	○
Past history (interstitial pneumonia)	×	○
Complication (infection)	×	○
Complication (malignant tumor)	○	×
Complication (hepatitis B)	○	×
Complication (hepatitis C)	○	×
Complication (diabetes mellitus)	×	○
Smoking history	○	○
Family history of malignant tumors (including lymphoma)	○	○
History of MTX use (Within 3 months prior to the start of survey)	○	○
MTX criteria	○	○
History of oral steroid use (Within 3 months prior to the start of survey)	○	○
History of tacrolimus use (Within 3 months prior to the start of survey)	○	○
Past use of biological agents (Within 3 months prior to the start of survey)	○	○

Covariats	Malignant tumor	Serious infection
Initial dose of Xeljanz	○	○
Neutrophil count	○	○
Lymphocyte count	○	○
Prophylactic administration to prevent tuberculosis	×	○
Prophylactic administration to prevent pneumocystis jiroveci pneumonia	×	○
Prophylactic administration to prevent hepatitis B	×	○
DAS28	○	○

○: Applicable, ×: Not applicable

Covariates may be added or removed based on the results of the interim analyses of this survey and newly obtained findings. In that case, this plan will be revised.

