### 8.1.6. Group Comparison of Incidence Rate and Incidence Proportion of Specified Events

Specified events including initial malignancy, initial severe infection, and death will be compared between groups in terms of the following quantities:

- **Incidence ratio between the treatment groups and the 95% confidence interval**

$$\text{Incidence ratio} = \frac{a/\text{PT}_1}{b/\text{PT}_0}$$

95% confidence interval for incidence ratio

$$= \exp \left[ \left\{ \ln \left( \frac{a/\text{PT}_1}{b/\text{PT}_0} \right) \pm 97.5 \text{ percentile for standard normal distribution} \times \sqrt{\frac{1}{a} + \frac{1}{b}} \right\} \right]$$

Xeljanz group a: Number of patients with the event [patient], PT1: Duration of exposure [patient-year]

Control group b: Number of patients with the event [patient], PT0: Duration of exposure [patient-year]

- **Difference in incidence rates between treatment groups and its 95% confidence interval**

Difference in incidence rates [patient/100 patient-years]

$$= 100 \times \left( \frac{a}{\text{PT}_1} - \frac{b}{\text{PT}_0} \right)$$

95% confidence interval for difference in incidence rates [patient/100 patient-years]

$$= 100 \times \left\{ \left( \frac{a}{PT_1} - \frac{b}{PT_0} \right) \pm 97.5 \text{ percentile for standard normal distribution} \right. \\ \left. \times \sqrt{\frac{a}{PT_1^2} + \frac{b}{PT_0^2}} \right\}$$

- **Ratio of incidence proportions between treatment groups and its 95% confidence interval**

$$\text{Ratio of Incidence proportions} = \frac{a/N_1}{b/N_0}$$

95% confidence interval for ratio of incidence proportions

$$= \exp \left[ \left\{ \ln \left( \frac{a/N_1}{b/N_0} \right) \pm 97.5 \text{ percentile for standard normal distribution} \right. \right. \\ \left. \left. \times \sqrt{\frac{1}{a/N_1} + \frac{1}{b/N_0}} \right\} \right]$$

Xeljanz group

$N_1$ : Number of patients included in the analysis [patient]

Control group

$N_0$ : Number of patients included in the analysis [patient]

- **Difference in incidence proportion between the treatment groups and the 95% confidence interval**

$$\text{Difference in incidence proportion [%]} = 100 \times \left( \frac{a}{N_1} - \frac{b}{N_0} \right)$$

95% confidence interval [%] for the difference in incidence proportion

$$= 100$$

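### The readable SAP text lists no covariate-adjusted Xeljanz-versus-control comparison of deaths in 8.2.3.1.3, although 8.1.6 names death among the events compared by adjusted methods and 6.3 gives no covariates for it

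*SAP*

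**What the plan says.** SAP 2.1 describes the design: "This survey is a non-interventional study". SAP 6.1.1 lists death and time to death among the endpoints for comparing the two groups, and 8.2.3.1.3 names deaths over the overall observation period as the primary evaluation.

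Under Mortality rate, 8.2.3.1.3 gives the rate in each group and then: "In addition, the incidence ratio and the 95% confidence interval and the difference in incidence rate and the 95% confidence interval will be calculated". It asks for the same pair of measures on incidence proportions, a Kaplan-Meier summary by group, and an SMR for each group against the Japanese population by sex, age and calendar year.

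The general methods are wider. SAP 8.1.6 opens: "Specified events including initial malignancy, initial severe infection, and death will be compared between groups in terms of the following quantities". Its list includes pooled (stratified) ratios and differences, the covariate-adjusted Cox hazard ratio and propensity scores. The covariates for these come from 6.3, which covers two endpoints only: "candidate covariates related to the development of malignant tumors and serious infections are shown below".

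On the status of all tests, SAP 4 states: "Since this survey is not a confirmatory study, statistical tests will be exploratory".

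**The concern.** Control patients are selected according to routine prescribing (Protocol 6.4), so the groups may differ in smoking, steroid use, comorbidity and disease severity, all of which may bear on mortality. The SAP recognises this for malignant tumors and serious infections and adjusts for it. A programmer who follows 8.2.3.1.3 as written would produce an unadjusted mortality ratio that stands in the same report as weighted hazard ratios for the other two endpoints. A programmer who follows 8.1.6 would need an adjusted ratio for death but would find no covariates for it in 6.3. The first figure could mix drug effect with patient selection. The second would depend on choices made after the data are known.

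**Working it through.** **1. The three event sections side by side (readable text)**

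| Between-group item | Malignant tumors (8.2.3.1.1) | Serious infections (8.2.3.1.2) | Deaths (8.2.3.1.3) |
|---|---|---|---|
| Crude rate and proportion ratios and differences | yes | yes | yes |
| Kaplan-Meier by group | yes | yes | yes |
| Pooled over single covariates | yes | yes | not listed |
| Covariate-adjusted Cox hazard ratio | yes | yes | not listed |
| Propensity-weighted hazard ratio, balance check | yes | yes | not listed |
| Comparison with the Japanese population | SIR | none | SMR |
| Covariate column in 6.3 | yes | yes | none |

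The death section refers to 8.1.5 for rates and proportions, to 8.1.4 for Kaplan-Meier, and to 8.1.6 for the SMR only. Section 8.1.4 mentions a Cox model conditionally, if a model analysis is performed. The death section does not say that one will be.

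**2. The plan's only planning figure.** Inputs from the Protocol's sample size rationale: 4000 patients, 1.16 malignant tumors per 100 person-years, about 50% drop-out at 3 years. With linear drop-out, mean follow-up is 3 × (1 − 0.5/2) = 2.25 years. Then 4000 × 2.25 = 9000 person-years, and 9000 × 0.0116 = 104.4, which matches the stated 104. For 2000 controls, 2000 × 2.25 = 4500 person-years. The documents give no death rate and no baseline difference between the groups, so everything below rests on assumed values.

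**3. Expected deaths and precision.** Assume a true ratio of 1 and the same death rate in both groups. The 8.1.6 interval is exp(±1.96 × √(1/a + 1/b)).

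| Deaths per 100 person-years (assumed) | Xeljanz / control deaths | 95% interval around 1 |
|---|---|---|
| 0.3 | 27 / 13.5 | 0.52 to 1.92 |
| 0.5 | 45 / 22.5 | 0.60 to 1.66 |
| 1.0 | 90 / 45 | 0.70 to 1.43 |
| 1.5 | 135 / 67.5 | 0.75 to 1.34 |

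**4. Shift from one unadjusted binary risk factor.** Bias factor = [p1(RR − 1) + 1] / [p0(RR − 1) + 1], where p1 and p0 are the prevalences in the two groups and RR is the factor's mortality risk ratio.

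- 50% versus 40%: RR 2 gives 1.5/1.4 = 1.07; RR 6 gives 3.5/3.0 = 1.17. Reversed: 0.93 and 0.86.
- 50% versus 30%: RR 2 gives 1.5/1.3 = 1.15; RR 6 gives 3.5/2.5 = 1.40. Reversed: 0.87 and 0.71.

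**5. Chance that the crude interval excludes 1 with no drug effect.** Xeljanz deaths are multiplied by the bias factor and control deaths left unchanged. With z = ln(bias)/√(1/a + 1/b), the chance is 1 − Φ(1.96 − z) + Φ(−1.96 − z).

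| Bias factor | 0.5 deaths per 100 person-years | 1.0 deaths per 100 person-years |
|---|---|---|
| none | 5% | 5% |
| 1.1 | 6.6% | 8.3% |
| 1.4 | 27.8% | 49.1% |

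Example: bias 1.4 at 0.5 per 100 gives a = 63 and b = 22.5, so z = 0.336/0.246 = 1.37 and the chance is 27.8%.

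**6. Room for covariates.** The two lists in 6.3 together hold 29 items. Without initial Xeljanz dose, neutrophils, lymphocytes and DAS28, 25 remain. At 0.3 to 0.5 deaths per 100 person-years, total deaths are 40.5 to 67.5, or 1.6 to 2.7 per covariate. A full Cox model on the merged list would be overloaded.

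**The case against.** Several counter-arguments have force.

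- **Redaction.** A blacked-out block follows the SMR text, and the change log places a sensitivity analysis of the group comparison in 8.2.3.1.4, which cannot be read. A reader might infer that the plan contains no adjusted mortality analysis at all. The documents do not support that. The point is limited to the readable text, where the crude ratios and the missing covariate column in 6.3 can both be seen.
- **Section 8.1.6.** It names death, its list includes the adjusted methods, and SAP 3 says that the final analysis will carry out everything the plan specifies. On this reading the adjusted comparison is already required. But without covariates it cannot be carried out as specified, and 8.2.3.1.3 does not ask for it. The sections disagree.
- **The SMRs.** To say that deaths are compared with crude figures alone would be wrong, because each SMR is standardised for sex, age and calendar year. This stands, and it is why the illustration above does not use an age imbalance. However, each SMR compares one group with the general population. Two SMRs are not strictly comparable with each other, and neither accounts for smoking, steroids, comorbidity or disease severity.
- **Objectives.** The comparative objective (Protocol 1, SAP 2.2) names malignant tumors and serious infections only, Protocol 8.3 places the adjusted hazard ratio under those two, and all tests are exploratory. This lowers the weight of the point. It does not make an unadjusted ratio from a non-randomised comparison easier to interpret.

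**Conclusion.** The point holds in limited form. In the readable SAP, every direct Xeljanz-versus-control measure of death in 8.2.3.1.3 is unadjusted, and this section does not agree with 8.1.6 and 6.3. The mortality ratio is open to confounding. A reader might go further and infer that it is biased, or biased against or in favor of Xeljanz. Without a death rate or a baseline difference in the documents, neither can be said.

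The size is illustrative only: a factor of 1.07 to 1.40, or 0.93 to 0.71 if reversed, for one binary risk factor under the assumed prevalences and risk ratios. At the upper end, a 95% interval would exclude 1 in 27.8% to 49.1% of cases with no drug effect, at 0.5 to 1.0 deaths per 100 person-years on 9000 and 4500 person-years. At a factor of 1.1 the rise is small, to 6.6% to 8.3%. The change is worth making, but it does not affect the survey's two stated comparative endpoints.

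**What to change.** Bring 8.1.6, 6.3 and 8.2.3.1.3 into agreement:

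1. Add a death column to 6.3, limited to baseline items recorded in both groups: for example sex, age, weight, RA stage, class and duration, smoking, history of malignancy, infection, lung, cardiovascular and renal disease and diabetes, and prior MTX, steroid and tacrolimus use. Leave out Xeljanz-only items such as initial dose and DAS28. Merging the two existing lists is not enough: cardiovascular and renal history are recorded (SAP 11.1.2) but appear in neither list.
2. Add to 8.2.3.1.3 a propensity-weighted hazard ratio for death over the overall observation period, using the weights and balance tables already described for malignant tumors. Add a Cox model with few covariates, in view of the likely number of deaths.
3. Label the crude ratios and differences as descriptive.
4. If 8.2.3.1.4 already holds an adjusted death analysis, refer to it from 8.2.3.1.3 and state its covariates.

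The cost is SAP text, one new propensity model and a wider interval than the crude one. No new data are needed. The weighting, Cox and imputation methods are already specified, but this is more than a rerun, because a covariate set for death has to be chosen. The version 10.0 entry in the change log shows that the database has been released, so date the addition and label it as added afterwards.

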#### **8.2.3.2. Safety analysis in the Xeljanz group**

Statistical analyses in this section will be performed in the safety analysis set in the Xeljanz group. Adverse drug reactions and adverse events will be analyzed for all those reactions or events that developed during the survey period, and those that developed by 6 months after the start of Xeljanz.

- Development of adverse drug reactions**

The number of patients with adverse drug reactions and the incidence proportion will be calculated for each SOC and PT.

The number of patients with adverse drug reactions and the incidence proportion will also be calculated for each SOC and PT for new patients in whom treatment started from this survey, patients who participated in clinical trials, and patients administered Xeljanz at other institutions. Furthermore, the calculation will also be performed for the subpopulations that do and do not meet the MTX criteria in the Xeljanz group.

- Development of serious adverse drug reactions**

The number of patients with serious adverse drug reactions and the incidence proportion will be calculated for each SOC and PT.

The number of patients with serious adverse drug reactions and the incidence proportion will also be calculated for each SOC and PT for new patients in whom treatment started from this survey, patients who participated in clinical trials, and patients administered Xeljanz at other institutions. Furthermore, the calculation will also be performed for the subpopulations that do and do not meet the MTX criteria in the Xeljanz group.

- **Development of serious adverse events**

The number of patients with serious adverse events and the incidence proportion will be calculated for each SOC and PT.

- **Development of adverse events**

The number of patients with adverse events and the incidence proportion will be calculated for each SOC and PT.

- **Development of adverse drug reactions in patients included in and excluded from the safety analysis set**

The number of patients with adverse drug reactions among patients for whom the CRF is collected and who are included in and excluded from the safety analysis set and the incidence proportion will be calculated for each SOC and PT.

- **Details of adverse drug reactions by event**

The number of patients with adverse drug reactions and the incidence proportion will be calculated for each SOC and PT for each category in Table 8.

If an adverse drug reaction with the same PT occurs multiple times in the same patient, the order of precedence in [Table 8](#) will be applied.

